### **6.8.6. Vital Signs and Other Physical Findings**

All vital signs data, height and weight will be summarized and listed by visit/time points and cohort for patients on therapy.

### **6.8.7. Electrocardiograms**

Electrocardiogram (ECG) data will be summarized by visit and parameter for patients on therapy. Any abnormal ECG data will be listed by patient. Number and percentage of subjects with AEs that could be associated with abnormal ECGs will be presented, if appropriate.

If available, the number of patients meeting the following criteria with respect to QTc will be presented for maximum on-study value:

- QTc, >480 to 500 msec, and >500 msec and delta QTc >30 to 60 msec, and >60 msec.

All instances when a patient met the above criteria will be listed. Maximum absolute and change from baseline QTc data will be summarized as a continuous variable. Frequency of patients with Normal ( $\leq 480$  msec) or High ( $>480$  msec) QT/QTc interval at baseline and post baseline nominal time points will be summarized by shift table. Summaries of other ECG parameters (for example, RR, PR, and QRS) will be presented, if appropriate. A QT-concentration analysis of change from baseline in QTcF versus serum concentration may be performed, if deemed appropriate.

Lilly will review ECG data and monitor cardiac events/deaths during the course of the study.

## **6.9. Pharmacokinetic Analyses**

The sampling schedule for drawing blood samples for LY2510924 and Durvalumab for determination of LY2510924 and Durvalumab concentrations is provided in Attachment 4 of the protocol. Serum concentrations of Durvalumab prior to infusion ( $C_{min}$ ) and post-end of infusion will be summarized using descriptive statistics. Pharmacokinetic parameters for LY2510924 will be computed by standard noncompartmental methods using PhoenixTM WinNonlin® or equivalent program on a computer that meets or exceeds the minimum system requirements for this program. The primary parameters for analysis will be area under the concentration-time curve (AUC) of LY2510924. Other noncompartmental parameters, such as time of half-life ( $t_{1/2}$ ), apparent clearance (CL/F), and apparent volume of distribution (V/F) may be reported.

Population PK analyses for LY2510924 may be conducted using a population PK approach as deemed necessary by Global PK/PD management. Planned PK analyses are specified in separate standalone NCA and popPK/PD analysis plans as appropriate. The version of any software used for the analysis will be documented and the program will meet the Lilly requirements of software validation. It is possible that other equivalent pharmacokinetic/graphing/scripting software programs may be utilized if appropriate, warranted, and approved by Global PK/PD management for generating PK and PK/PD tables, figures, and listings. Upon completion of quality control and quality review procedures, all documentation will be collected and filed in a Lilly-approved repository. All PK and PK/PD analysis, and creation of table, figures, and listings will be the

responsibility of Lilly Global PK/PD & Pharmacometrics group based on applicable functional Standard Operating Procedures and software approved by this group's management.

### **6.10. Biomarker Analyses**

Exploratory biomarkers will be summarized and assessed for correlations with clinical outcomes. Biomarker relationships by tumor type, changes in biomarker levels at baseline and over time, and differences among dose levels or exposure will be explored as possible.

### **6.11. Pharmacokinetic/Pharmacodynamic Analyses**

The relationship between LY2510924 exposure and selected efficacy, safety outcomes, and biomarkers may be explored if relevant.

### **6.12. Immunogenicity Analyses**

Immunogenicity incidence will be tabulated, and correlation to MEDI4736, activity, and safety will be assessed, as appropriate, respectively. The measures that will be analyzed include baseline presence and level of ADA, treatment-emergent ADA, levels of neutralizing ADA, and incidence and levels of ADA related to IRRs.

### **6.13. Efficacy Analyses**

Tumor response data will be tabulated by cohorts. Particularly, the antitumor effect will be summarized by the objective response rate (ORR) and disease control rate (DCR) by cohort and overall. Mean, median, range, and exact 95% confidence intervals (CI) will be provided. Reported lesion measurement data, including sum of target lesions, change and/or percent change from baseline sum and smallest sum (nadir) at each visit will be listed for all patients on therapy. Investigator-determined response by cycle will be listed.

Time-to-event variables, such as progression-free survival (PFS), time to response (TTR), duration of response (DoR) and overall survival (OS) will be listed and summarized. For all time-to-event variables, the Kaplan-Meier method (Kaplan and Meier 1958) will be used to estimate the survival curves, medians with 95% CI, and survival rates at various time points if applicable. For Phase 1b, time-to-event variables will be summarized by different cohorts.

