#### **6.13.1. Efficacy Analysis Variables (RECIST v.1.1)**

Definition of efficacy analysis variables are listed alphabetically.

**Disease Control Rate** is defined as the proportion of treated patients achieving a best overall response of complete response (CR), partial response (PR), or stable disease (SD) per RECIST v.1.1. Patients who do not have any postbaseline tumor response assessments for any reason are considered non-responders and are included in the denominator when calculating the response rate.

**Note.** Best overall response is the best response recorded from the start of treatment until disease progression, in the order of CR, PR, SD, PD, and NE.

**Duration of Response** is defined from the date of first documented CR or PR that is subsequently confirmed (responder) to the date of objective progression or the date of death due to any cause, whichever is earlier. If a responder is not known to have died or have objective progression, then the patient will be censored at the date of last evaluable tumor assessment.

**Objective response rate** is defined as the proportion of treated patients achieving a best overall response of PR or CR per RECIST v.1.1. Patients who do not have any postbaseline tumor response assessments for any reason are considered non-evaluable and are included in the denominator when calculating the response rate.

**Overall survival** is defined as time from the date of first treatment to the date of death from any cause. For each patient who is not known to have died as of the data-inclusion cut-off date for a particular analysis, OS will be censored for that analysis at the date of last contact prior to the data-inclusion cut-off date (contacts considered in the determination of last contact date include AE date, lesion assessment date, visit date, and last known alive date).

**Progression-free survival** is defined as the time from the date of first treatment until the date of radiographic documentation of progression (as defined by RECIST v. 1.1) based on investigator assessment or the date of death due to any cause, whichever is earlier.

**Time-to-response** is the time from the date of first study treatment until the first evidence of a confirmed CR or PR.

[Table CXAD.6.2](#) lists rules for determining date of progression or censor for PFS. The censoring is taken in the following order:

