### **6.13.2. Efficacy Analysis Variables (RECIST v1.1 with confirmatory scan for disease progression)**

For Study CXAD, RECIST v1.1 with confirmatory scan for disease progression (denote it as RECISTc for simplicity) will be adapted to account for the unique tumor response characteristics seen with treatment of immuno-oncology therapy. RECISTc will be applied as detailed in the study protocol, and the resulting data will be included in the clinical database.

**Objective response rate (RECISTc)** is defined as the proportion of treated patients achieving a best overall response of PR or CR per RECISTc. Particularly, the best overall response by RECISTc (denoted as ORRc) closely related to confirmed response by RECIST v1.1. ORRc further captures responses after unconfirmed PD and it does not require confirmation. For example:

- If the best response by RECIST is CR, then the best response by RECISTc is CR.
- If the best response by RECIST is PR, SD, or PD, the best response by RECISTc is the best response over the initial assessment (prior to PD by RECISTc) and the confirmation stage.

Overall, the best response by RECISTc should be the same or better than the best response by RECIST criteria. In addition, patients who do not have any postbaseline tumor response

assessments for any reason are considered non-evaluable and will be included in the denominator when calculating the response rate.

[figure not shown]
**PFSc:** The date from the treatment started date to the time of confirmed PD (PDc) assessed by RECISTc.

- If the initial PD is confirmed at the very next scan (consecutive PD) then the date of PDc is the initial PD date by RECIST v1.1.
- If the initial PD is unconfirmed at the very next scan (non-consecutive PD), then the date of PDc is the date of second PD.

[figure not shown]
**Duration of response by RECISTc:** The duration of response is defined from the date measurement criteria for CR or PR (whichever is first recorded) are first met to the date of PDc or the date of death due to any cause, in the absence of an observed PDc.

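### Kaplan-Meier is planned for time to response in all treated patients with no rule for progression or death before response; under the usual censoring it would overstate the response probability and place the median too early

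*SAP*

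**What the plan says.** SAP 6.13 names four variables: "Time-to-event variables, such as progression-free survival (PFS), time to response (TTR), duration of response (DoR) and overall survival (OS) will be listed and summarized". The next sentence sets the estimator for all of them: "For all time-to-event variables, the Kaplan-Meier method" is to supply curves and medians with 95% intervals, followed by "survival rates at various time points if applicable". Protocol 10.9 and the protocol synopsis also list time to response and name Kaplan-Meier.

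SAP 6.13.1 gives TTR one sentence: it "is the time from the date of first study treatment until the first evidence of a confirmed CR or PR". That sentence states no population, no censoring date for patients without a response, and no treatment of progression or death before response.

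The other three variables are handled differently. SAP 6.13.1 says that Table CXAD.6.2 "lists rules for determining date of progression or censor for PFS". Duration of response is restricted to responders and censored at the last evaluable tumor assessment. Overall survival is censored at last contact. SAP 6.3 runs efficacy analyses on everyone who received at least one dose.

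The response window also matters. Under RECIST v1.1, "Best overall response is the best response recorded from the start of treatment until disease progression". Under RECIST v1.1 with a confirmatory scan (RECISTc, SAP 6.13.2), "ORRc further captures responses after unconfirmed PD and it does not require confirmation". No TTR is defined under RECISTc.

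**The concern.** For progression-free survival, overall survival and duration of response, death is part of the event, so Kaplan-Meier is a natural choice. For TTR, death without response removes the patient from any possibility of the event. Under the RECIST v1.1 response window, progression does the same. These are competing events.

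If such patients are censored, Kaplan-Meier treats them as still able to respond at the rate seen in those who remain at risk. The curve then describes response in a setting where nobody progresses or dies. With about 15 patients per expansion arm, few remain at risk after the first scans, and each late response produces a large step. One report could show a TTR curve well above the ORR for the same patients, and a median time to response in an arm where most patients never respond.

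**Working it through.** **The plan's own figures.** The documents give no expected median, rate or event count for TTR, so there is nothing to reproduce on that variable. The nearest figures are the exact 95% limits for N = 15 (Protocol Table CXAD.10.1, SAP Table CXAD.5.1). They recompute correctly; for 3/15 the interval is 0.0433 to 0.4809, printed as 0.04 to 0.48.

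**Inputs from the documents.** About 15 patients per expansion arm (SAP 5.1); imaging every 8 weeks (Protocol 8.1); all treated patients in the efficacy population (SAP 6.3).

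**Assumed inputs.** The response and progression counts and their timing, and censoring of non-responders at progression or death. At a tied scan date, responses are counted before censorings.

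**Formulas.** At scan t, let n be the number at risk, r the responders and p the patients who progress or die.
- 1-KM = 1 − Π(1 − r/n).
- Cumulative incidence = Σ S(t−)·r/n, where S is the probability of still being free of response, progression and death.

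**Example A: 3 of 15 respond.**

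| Week | n | r | p | 1-KM | Cumulative incidence |
|---|---|---|---|---|---|
| 8 | 15 | 1 | 7 | 0.067 | 0.067 |
| 16 | 7 | 1 | 3 | 0.200 | 0.133 |
| 24 | 3 | 1 | 2 | 0.467 | 0.200 |

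At week 24, 1-KM = 1 − (14/15)(6/7)(2/3) = 0.467. Cumulative incidence = 1/15 + (7/15)(1/7) + (3/15)(1/3) = 3/15 = 0.200, which equals the ORR.

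**Example B: also 3 of 15, with slightly earlier progression** (p = 8, 3, 1, so n = 15, 6, 2). 1-KM = 1 − (14/15)(5/6)(1/2) = 0.611. Kaplan-Meier now reports a median of 24 weeks although 12 of 15 patients never respond. The value lies above the exact upper limit of 0.48 for the ORR.

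**Example C: 9 of 15 respond** (r = 4, 3, 2; p = 3, 2, 1; n = 15, 8, 3).
- 1-KM: 1 − 11/15 = 0.267; 1 − (11/15)(5/8) = 0.542; 1 − (11/15)(5/8)(1/3) = 0.847.
- Cumulative incidence: 4/15 = 0.267; 7/15 = 0.467; 9/15 = 0.600.
- Median: 16 weeks by Kaplan-Meier, 24 weeks by cumulative incidence.

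**Range under constant hazards.** Let the median time to the first of response, progression or death be m months, λ = ln 2/m, and π the share of patients whose first event is a response. Then 1-KM(t) = 1 − exp(−πλt) and cumulative incidence(t) = π(1 − exp(−λt)). The Kaplan-Meier median is m/π. The cumulative-incidence median is −ln(1 − 0.5/π)/λ, and exists only if π > 0.5.

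| π | m | 1-KM, 6 months | Cumulative incidence, 6 months | KM median | Cumulative-incidence median |
|---|---|---|---|---|---|
| 0.2 | 2 | 0.340 | 0.175 | 10.0 | never reached |
| 0.2 | 4 | 0.188 | 0.129 | 20.0 | never reached |
| 0.6 | 2 | 0.713 | 0.525 | 3.3 | 5.2 |
| 0.6 | 4 | 0.464 | 0.388 | 6.7 | 10.3 |

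The direction is the same in every row: the probability is too high and the median too early, or present when it should not be. The size depends on how fast patients progress.

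**The case against.** The strongest reply is that the SAP nowhere says progressors or deaths are censored for TTR. A reader might infer that it prescribes such censoring. It does not; it is silent, and the bias depends on how the silence is filled. That stands. Two ways of filling it do no harm. If TTR is computed in responders only, nobody is censored. If non-responders stay at risk to the end of complete follow-up, 1-KM equals the cumulative incidence.

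The responders-only reading has some support, since TTR has a value only for a confirmed responder. But the SAP writes that restriction into duration of response and not into TTR, and SAP 6.3 puts all treated patients in efficacy analyses. Censoring at last assessment, as the SAP does for progression-free survival and duration of response, is the likely default for a programmer.

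The SAP's qualifier about applicability follows the rates at time points. Its reach is arguable, and it does not clearly exempt TTR curves and medians.

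A reader might also take progression always to end the chance of response. That holds for RECIST v1.1 best response, the only basis on which TTR is defined. It does not hold for RECISTc, which counts responses after an unconfirmed progression. Death is final under both.

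Finally, the consequence is limited. The analyses are descriptive, no decision rule uses TTR, and individual times will be listed.

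**Conclusion.** The point holds as a gap in specification: Kaplan-Meier is prescribed for TTR, the population is all treated patients, and the rule for progression or death before response is missing. Under censoring of non-responders, the response probability is overstated: 0.47 or 0.61 against 0.20 in Examples A and B, and 0.19 to 0.34 against 0.13 to 0.18 at 6 months with a 20% response share. All of these rest on assumed rates and timing.

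A reader might expect the median time to response to come out too long. Against cumulative incidence it comes out too early, because a curve that is too high crosses one half sooner. The Kaplan-Meier median is longer only than the median among responders (m, or 2 to 4 months, in the constant-hazard cases), which is a different quantity.

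Nor does the problem extend to the ORR, a proportion of treated patients with an exact interval. This is worth correcting before the tables are programmed, but it touches only a descriptive secondary variable.

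**What to change.** Remove TTR from the Kaplan-Meier sentence in SAP 6.13. In SAP 6.13.1, state that TTR is summarised as median and range among confirmed responders.

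If a curve over all treated patients is wanted, specify a cumulative incidence function (Aalen-Johansen) with death and progression per RECIST v1.1 as competing events. If a RECISTc version is also wanted, say which progression closes the response window.

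Align Protocol 10.9 and the synopsis at the next amendment. Alternatively, describe the change in the clinical study report, which SAP 6.1 allows when no principal feature of the protocol changes. The cost is a few sentences; no data collection, sample size or other analysis is affected.

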#### **6.13.1. Efficacy Analysis Variables (RECIST v.1.1)**

Definition of efficacy analysis variables are listed alphabetically.

**Disease Control Rate** is defined as the proportion of treated patients achieving a best overall response of complete response (CR), partial response (PR), or stable disease (SD) per RECIST v.1.1. Patients who do not have any postbaseline tumor response assessments for any reason are considered non-responders and are included in the denominator when calculating the response rate.

**Note.** Best overall response is the best response recorded from the start of treatment until disease progression, in the order of CR, PR, SD, PD, and NE.

**Duration of Response** is defined from the date of first documented CR or PR that is subsequently confirmed (responder) to the date of objective progression or the date of death due to any cause, whichever is earlier. If a responder is not known to have died or have objective progression, then the patient will be censored at the date of last evaluable tumor assessment.

**Objective response rate** is defined as the proportion of treated patients achieving a best overall response of PR or CR per RECIST v.1.1. Patients who do not have any postbaseline tumor response assessments for any reason are considered non-evaluable and are included in the denominator when calculating the response rate.

**Overall survival** is defined as time from the date of first treatment to the date of death from any cause. For each patient who is not known to have died as of the data-inclusion cut-off date for a particular analysis, OS will be censored for that analysis at the date of last contact prior to the data-inclusion cut-off date (contacts considered in the determination of last contact date include AE date, lesion assessment date, visit date, and last known alive date).

**Progression-free survival** is defined as the time from the date of first treatment until the date of radiographic documentation of progression (as defined by RECIST v. 1.1) based on investigator assessment or the date of death due to any cause, whichever is earlier.

**Time-to-response** is the time from the date of first study treatment until the first evidence of a confirmed CR or PR.

[Table CXAD.6.2](#) lists rules for determining date of progression or censor for PFS. The censoring is taken in the following order:

- If a patient does not have a baseline disease assessment, then the PFS time will be censored at the treatment starting date, regardless of whether or not objective progressive disease (PD) or death has been observed for the patient; otherwise,
- If a patient is not known to have died or have investigator-assessed PD as of the data-inclusion cut-off date for the analysis, the PFS time will be censored at the date of last postbaseline adequate radiological tumor assessment, or at the date of first treatment if the patient does not have any postbaseline adequate radiological assessment.

**Note.** If there are multiple dates associated with one radiological tumor assessment, the assessment date will be set to the first date when the overall response is PD and the last date otherwise. A radiological tumor assessment is considered adequate if its response is among CR, PR, SD, or PD.

$$\text{PFS (day)} = \text{Date of progression / censor} - \text{date of first treatment} + 1$$

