Patients who have discontinued from combination treatment will enter the Post Discontinuation Follow-Up Period with visits at approximately 30, 60, and 90 days. If a patient has discontinued treatment for reasons other than disease progression, tumor assessments should continue every 8 weeks until confirmed disease progression occurs, initiation of a new anticancer therapy, the patient dies, or is lost to follow-up. Patients will be followed for survival at least every 12 weeks (± 7 days) until death or study completion. This follow-up may occur through a phone call, email, or visit by the patient or the patient's caretaker.

Refer to [Attachment 1](#) for the Study Schedule.

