8.1.2.2.3. Follow-Up Visit

All AEs and SAEs, regardless of relatedness to study drug(s) or protocol procedures, occurring during the 30-day, 60-day, and 90-day safety follow-ups occurring after last dose of combination treatment must be reported to Lilly or its designee ([Attachment 1](#)).

Following the 30-, 60-, and 90-day follow-up assessments, patients who discontinue from study treatment for progressive disease will be followed only for survival, unless there is an ongoing AE or SAE that is possibly related to study drug or protocol procedures. In this instance, the patient should be followed in subsequent follow-up visits until the event is resolved, the event is no longer considered to be drug-related, the event becomes stable or returns to baseline, a new treatment is initiated for the patient, or the patient dies or is lost to follow-up. For patients who have discontinued study treatment for reasons other than progressive disease, these patients will be followed for survival, progression-free survival (PFS), time and duration of response, and best overall response (BOR), unless they have started another treatment. In that case, the patient will only be followed for survival. Patients with an ongoing AE or SAE that is possibly related to

study drug or protocol procedures will be followed until the event is resolved, unless a new treatment is started.

If it is deemed to be in the best interest of the patient to start a new anticancer treatment prior to the scheduled end of the 90-day follow-up visit, the follow-up visit duration may be shortened. In this case, the follow-up assessments should be completed prior to the initiation of the new therapy.

After the 90-day follow-up visit, AEs are not required to be reported unless the investigator feels the AEs were related to either study drug or a protocol procedure. If an investigator becomes aware of an SAE believed to be related to protocol procedures or study drug, the investigator should report the SAE to the sponsor, and the SAE will be entered in the Lilly Safety System.

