**Table CXAD.6.2. Rules for Determining Date of Progression or Censor for Progression-Free Survival**

Rule	Situation	Date of Progression or Censor	Outcome
1	No baseline tumor assessments	Date of first treatment	Censored
2	No postbaseline assessments and no death	Date of first treatment	Censored
3	No documented progression and no death (with a postbaseline tumor assessment)	Date of last adequate tumor assessment	Censored
4	Patient lost to follow-up (or withdrew consent from study participation) before documented progression or death	Date of last adequate tumor assessment	Censored
5	Documented progression	Date of documented progression  If a tumor assessment was done on multiple days, use the earliest date for that visit.	Progressed
6	Death without documented progression	Date of death	Progressed
7	Documented progression or death after missing $\geq 2$ consecutive postbaseline tumor assessments	Date of last adequate tumor assessment before missed assessments or date of first treatment, whichever is later	Censored

Note: Progression-free survival and associated outcome is determined by the earliest of the dates above, if more than 1 situation applies.

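### Duration of response counts a death or progression after missed scans as an event, while PFS censors the same event (SAP 6.13.1 and Table CXAD.6.2, rule 7)

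*SAP*

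**What the plan says.** **DoR.** SAP 6.13.1 starts DoR at the first documented complete or partial response that is later confirmed, and runs it "to the date of objective progression or the date of death due to any cause, whichever is earlier". It gives one censoring rule, for responders with neither event: "then the patient will be censored at the date of last evaluable tumor assessment".

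**PFS.** The same section introduces Table CXAD.6.2 as a table that "lists rules for determining date of progression or censor for PFS". Rule 6 makes a death without documented progression an event on the date of death. Rule 7 covers "Documented progression or death after missing" two or more consecutive postbaseline assessments. It censors at the "Date of last adequate tumor assessment before missed assessments or date of first treatment, whichever is later". The note under the table lets the earliest date govern when several rules apply, so rule 7 overrides rule 6. Rule 7 appears only in the table, not in the ordered censoring list that precedes it.

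**Follow-up.** Under Protocol 6.2, patients who stop treatment without progression are scanned every 8 weeks until confirmed progression, "initiation of a new anticancer therapy, the patient dies, or is lost to follow-up". Survival contact continues at least every 12 weeks. Protocol 8.1.2.2.3 follows such patients for PFS and response duration unless another treatment has started: "In that case, the patient will only be followed for survival".

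**RECISTc.** SAP 6.13.2 ends DoR at confirmed progression "or the date of death due to any cause, in the absence of an observed" confirmed progression. It states no censoring rule for this DoR, and none for the PFS version, PFSc.

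**The concern.** Rule 7 reflects a decision not to credit a patient with progression-free time across a long gap without scans. DoR needs that protection just as much, because a response that nobody has assessed is not known to have continued. As written, a responder whose scans lapse and who dies much later is recorded as responding until death, while the PFS table shows the same patient censored at the last scan. A progression found after the gap produces the same mismatch.

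The route is plausible. An adverse event that requires stopping one drug stops both, so a responder can leave treatment without progression. Continued survival contact means that a later death will usually be known. If the patient has moved to another therapy, the recorded DoR also includes time on that therapy, although the protocol itself stops following response duration at that point. DoR will be summarised by Kaplan-Meier in arms of about 15 patients, so one such case can decide the reported median.

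**Working it through.** The plan gives no figure for DoR, so there is none to reproduce. The check applies both definitions to the same hypothetical patients.

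**Inputs**
- Scan interval: 8 weeks, or 56 days (Protocol 6.2). First evaluation at about 2 months (protocol synopsis), taken as day 57, then days 113, 169, 225, 281 and 337.
- First dose on day 1.
- PFS = end date − first treatment date + 1 (SAP 6.13.1). The SAP gives no day formula for DoR, so the same + 1 count is assumed.
- Response dates, last scans and deaths are illustrative assumptions.

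**Main case.** Partial response on day 57, confirmed at the last scan on day 113, later scans due but missed, death on day 393.
- Missed before death: days 169, 225, 281 and 337, so four. Rule 7 applies.
- PFS = 113 − 1 + 1 = 113 days, censored.
- DoR = 393 − 57 + 1 = 337 days, event.
- DoR with rule 7 applied = 113 − 57 + 1 = 57 days, censored.

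If progression rather than death is documented on day 393, the figures are the same.

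**Variations**

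| Response day | Last scan day | Death day | Scans missed | PFS (days) | DoR as written (days) |
|---|---|---|---|---|---|
| 57 | 113 | 193 | 1 | 193, event | 137, event |
| 57 | 113 | 226 | 2 | 113, censored | 170, event |
| 57 | 113 | 393 | 4 | 113, censored | 337, event |
| 113 | 169 | 282 | 2 | 169, censored | 170, event |
| 169 | 225 | 338 | 2 | 225, censored | 170, event |

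**General condition.** Let R be the response day, L the last scan day and D the day of death. Under rule 7, PFS = L and DoR = D − R + 1. DoR is the larger when D − L > R − 1, that is, when the gap from last scan to death exceeds the time from first dose to response. Two missed scans imply D − L > 112. For R = 57 (R − 1 = 56) and R = 113 (R − 1 = 112) the condition is then always met. For R = 169 it needs a gap above 168 days. With one missed scan or none, rule 6 applies to both endpoints and PFS is the longer.

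**Effect on the median.** Take the main-case patient with assumed co-responders.
- *Two others progress 16 and 24 weeks after response* (16 × 7 + 1 = 113 and 24 × 7 + 1 = 169 days). As written, events at 113, 169 and 337 give S = 2/3, 1/3 and 0, so the median is 169. With rule 7, the data 57+, 113, 169 give S = 1/2 at 113, so the median is 113 (midpoint convention: (113 + 169)/2 = 141). The median shortens.
- *One other progresses at 60 weeks* (60 × 7 + 1 = 421 days). As written, events at 337 and 421 give S = 1/2 at 337, so the median is 337 (midpoint convention: (337 + 421)/2 = 379). With rule 7, the data 57+, 421 give a median of 421. The median lengthens.

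**New anticancer therapy.** Suppose the main-case patient starts another therapy between days 169 and 225. Only the day-169 scan was due and missed. If scans after the new therapy are not missed, rule 7 is not triggered, and PFS is 393 − 1 + 1 = 393 days (event), longer than DoR. If they do count, PFS is 113 days (censored). The SAP does not say which. DoR is 337 days (event) either way.

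**The case against.** Several stronger conclusions might be drawn, and the documents do not support them.

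- **That a DoR longer than PFS is logically impossible.** A PFS censored at day 113 says only that PFS exceeds 113 days, which is compatible with a DoR of 337 days. The rules are inconsistent, not contradictory.
- **That the definition always favours the combination.** The affected patient's recorded response is lengthened, but the median can move either way, as shown above.
- **That PFS is certainly censored after a new therapy.** This depends on whether scans that are no longer required count as missed. For that group, the more basic gap is that neither endpoint has a new-therapy rule.
- **That the RECISTc section shows the same asymmetry.** It does not, because PFSc has no missed-scan rule either. Changing only the RECISTc DoR would create a mismatch.

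Counting death from any cause as the end of response also mirrors the SAP's basic PFS definition, and censoring such deaths discards events and may be informative. That is a real cost, but the SAP already accepted it for PFS.

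The case also needs a confirmed responder who leaves without progression, misses at least two scans and dies before cut-off. The final analysis comes about 6 months (SAP 6.15) or at most 12 months (Protocol 10.10) after the last patient of an arm starts. A last-enrolled patient would therefore not reach day 226 under the first timing or day 393 under the second. The problem is confined to patients enrolled earlier. Listings will let a reader see each responder. These points limit the impact but do not reconcile the two rules.

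**Conclusion.** The point stands as an inconsistency between two rules in the same SAP section. An event after two or more consecutive missed assessments is censored for PFS and counted for DoR, and the unassessed interval is reported as response. In the illustration, the patient's recorded response is 337 days as written, against 57 days (censored) under the PFS rule. Nothing elsewhere extends rule 7 to DoR: Protocol 10.9 gives no censoring rules. Protocol Attachment 10 ends response duration at recurrence or progression and does not mention death, so it does not settle the matter.

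For scans that were due and missed, this follows directly from the text, given the table's earliest-date note. For patients who start a new anticancer therapy, the finding is narrower: DoR includes time on the other therapy, and the PFS outcome is undefined. The sizes rest on assumed dates built on the 8-week schedule.

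The impact is modest. DoR is a descriptive secondary measure, no p-values are planned, and few responders are likely. The rule is still worth settling before analysis, because one responder can determine the median.

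**What to change.** 1. In SAP 6.13.1, state that DoR uses the same event and censoring rules as PFS in Table CXAD.6.2, including rule 7, with time counted from first documented response.
2. In the same place, state one rule for both PFS and DoR when progression or death follows the start of a new anticancer therapy: censor at the last adequate assessment before that therapy. This removes the question of whether scans no longer required count as missed.
3. In SAP 6.13.2, apply the same rules to both PFSc and the RECISTc DoR, with confirmed progression (PDc) as the progression event, so that no new mismatch is created.

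The cost is a few sentences. Design, sample size and tumour data collection are unchanged, and Attachment 1 already schedules collection of subsequent anticancer therapy. In the scenarios recalculated with rule 7 applied to DoR, DoR no longer exceeded PFS. The price is fewer DoR events and more censoring, which may be informative because scans often stop for reasons related to prognosis. The median may shorten or lengthen.
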